16.1.5 Specific Progression Criteria from Feasibility Study to Main Trial

- 20 sites trained, open and recruiting by the end of year 2
- 60 patients randomised by the end of year 2
- · Mean monthly recruitment of at least 6 patients in the last 4 months, as defined above

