16.2.5 Planned Final Analyses

The study will complete recruitment within 6 years and the analysis will take place when all patients have been followed-up for at least 5 years. Patients will continue with mammographic follow-up for a minimum of a further 5 and additional analysis will be undertaken.

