16.2.6 Sample Size Justification

The sample size calculation is based on the primary outcome of ipsilateral invasive breast cancer survival time. The primary analysis will be a comparison of the ipsilateral invasive breast cancer free rate between the Active Monitoring arm and Surgery Arm using a log-rank test for non-inferiority. The justification for the sample size is explained below.

Taking into account all published 5 year recurrence rates post-surgery for low risk disease, excluding contralateral disease and ipsilateral *in situ* disease, the projected recurrence rate (ipsilateral invasive breast cancer rate) at 5 years in the Surgery Arm is 2.5%. There is no relevant published data on 5 year ipsilateral invasive cancer rate in non-operated asymptomatic mammogram-detected low risk DCIS diagnosed by VACB and centrally reviewed. We have therefore based our non-inferiority calculation on extrapolation from the surgical data, estimates of overtreatment and what is judged to be a clinically relevant non-inferiority margin.

Page **36** of **48** Version 4.0, 15th March 2016

The non-inferiority design aims to show that not treating low risk DCIS with surgery is no worse (than a given margin) than treating with surgery. The primary outcome is ipsilateral invasive breast cancer free survival time and we will use a log-rank test for non-inferiority to determine whether no surgery is as good as surgery in these low risk DCIS patients by comparing the survival distributions of the two treatment groups. Because of the directional nature of the hypothesis, this non-inferiority test is one-sided. Jung *et al.* (49) derived an asymptotically exact sample size formula for the non-inferiority log-rank test to give the number of patients required to reject the null hypothesis that no surgery is worse than surgery, based on a given level of power and significance, assuming exponential survival distributions for both treatment groups, uniform patient accrual during a specified accrual period and set number of events during a period of follow-up, uniform censoring and no loss to follow-up.

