The one-sided Type I error rate is set at 5% and Type II error rate set at 20%, giving 80% power. The accrual period will be over 6 years and patients will be in follow-up for 5 years. The ipsilateral invasive breast cancer free rate at 5 years, based upon previous data (see above), is estimated to be 97.5%. The non-inferiority margin of maximal difference is determined to be 2.5%, therefore if the invasive breast cancer free rate at 5 years in the untreated group is not worse than 95%, then non-inferiority would be concluded since it falls within 2.5% of the treated population's invasive breast cancer free survival rate (97.5%). This decision was reached by the TMG, which comprises clinicians and patient representatives as well as statisticians. This non-inferiority margin equates to a hazard ratio of 2.02

The sample size calculation, given the above information estimates that 50 events will be sufficient to answer robustly the primary research question and it is estimated that 932 patients are required to achieve this number of events allowing for a 10% loss to follow-up/non-adherence rate.

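### The 50 events, 932 patients and 80% power in section 16.2.6 do not fit together: with both arms at the assumed 97.5%, 932 women give about 33–37 events and 65–69% power

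*Protocol*

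**What the plan says.** Protocol section 16.2.6 sizes the trial for a non-inferiority log-rank test. The error rates are explicit: "The one-sided Type I error rate is set at 5% and Type II error rate set at 20%, giving 80% power". For the control arm, "the projected recurrence rate (ipsilateral invasive breast cancer rate) at 5 years in the Surgery Arm is 2.5" per cent, that is, 97.5% event free. For the margin, "The non-inferiority margin of maximal difference is determined to be 2.5" percentage points, that is, 95% at 5 years, which the section equates to a hazard ratio of 2.02. Survival is taken as exponential, with "uniform patient accrual during a specified accrual period"; accrual lasts 6 years and follow-up 5. From this the section "estimates that 50 events will be sufficient to answer robustly the primary research question and it is estimated that 932 patients are required", the latter after allowing 10% for loss to follow-up or non-adherence.

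Section 16.2.5 sets the timing: "the analysis will take place when all patients have been followed-up for at least 5 years". It gives no minimum number of events. Section 16.2.4 plans descriptive interim reports only. The section does not say what 5-year rate in the Active Monitoring arm was used to turn 50 events into 932 patients.

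**The concern.** A non-inferiority sample size has two steps. The first finds the number of events needed for the stated power if the treatments are truly equal. The second finds how many patients will produce those events. Both must assume the same truth. Here the first step assumes equal arms, while the second appears to assume that Active Monitoring is at the margin, where its event rate is about twice as high. Too few patients are then recruited for the event target under the scenario for which power is quoted.

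The stake is the type II error. If Active Monitoring is as safe as surgery and the plan's rates are right, the trial would fail to show it about one time in three rather than one in five. Type I error is not affected.

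**Working it through.** **Inputs** (sections 16.2.5 and 16.2.6; 1:1 allocation from section 6.2.2): one-sided alpha 5%, power 80%, Surgery 97.5% and margin 95% event free at 5 years, exponential survival, uniform accrual over 6 years, analysis 5 years after the last entry (follow-up of 5 to 11 years per woman), 10% loss.

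**Hazards.** Surgery: −ln(0.975)/5 = 0.005064 per year. Margin: −ln(0.95)/5 = 0.010259 per year. Ratio 2.026, printed as 2.02.

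**Step 1, events.** Schoenfeld's formula with true hazard ratio 1: 4(1.645 + 0.842)²/(ln HR)².
- HR 2.02: 50.0 events.
- HR 2.026: 49.6 events.

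The plan's 50 is reproduced, and it rests on equal arms.

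**Step 2, patients.** Event probability with follow-up uniform on 5 to 11 years: p = 1 − (e^(−5h) − e^(−11h))/(6h).
- At 97.5%: p = 0.03966.
- At 95%: p = 0.07865.
- Average of the two: 0.05915.

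Patients = events / p / 0.9:

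| Assumed 5-year rates | Patients needed |
|---|---|
| Surgery 97.5%, Active Monitoring 95% | 49.6/0.05915/0.9 = 931.8 |
| Both arms 97.5% | 1,390 (49.6 events) to 1,401 (50 events) |
| Both arms 95% | 701 to 707 |

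With the rounded 50 events, the first row gives 939 when dividing by 0.9, or 930 when multiplying by 1.1. Two-sided Schoenfeld, Freedman's formula, exactly 5 years of follow-up per woman and a binary non-inferiority design were also tried; none returns 932.

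**What 932 women deliver if both arms are at 97.5%.** Power = Φ(ln 2.02 × √events / 2 − 1.645).
- 10% contribute nothing: 932 × 0.9 = 838.8 women; 838.8 × 0.03966 = 33.3 events; Φ(2.028 − 1.645) = 65%. Simulation of the non-inferiority log-rank test with 838 women gave 33.3 events and 65.1%.
- No loss: 932 × 0.03966 = 37.0 events; Φ(2.138 − 1.645) = 69%.
- Losses spread over time fall between: 34 to 36 events, 66 to 67%.

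**What 932 women deliver with Active Monitoring at 95%.** 838.8 × 0.05915 = 49.6 events, but the chance of concluding non-inferiority is then the type I error (simulated 4.9%).

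**Deaths.** The primary endpoint (section 2.2.2.1) also counts death from any cause, and the protocol gives no death rate. As an assumption, add the same death hazard to both arms, hold the margin at HR 2.02 and take 10% as lost:

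| Added deaths per year | Events | Power |
|---|---|---|
| none | 33 | 65% |
| 0.1% | 40 | 72% |
| 0.25% | 49 | 79% |
| 0.5% | 65 | 88% |

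**The case against.** The strongest reply is the endpoint. Women are 46 or older with no upper age limit, and every death is an event, so the real count may well exceed 33 and could reach 50. That stands, and a reader should not infer that the trial is bound to yield about 33 events or to be underpowered. It does not rescue the calculation: section 16.2.6 describes the 2.5% as an invasive recurrence rate, and if deaths come on top, the 97.5% and 95% rates no longer describe the endpoint as defined.

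Second, the Active Monitoring rate is not stated, and the match to 932 needs the unrounded hazard ratio. Both are true, so the mechanism is inferred. The conclusion does not depend on it: equal arms at 97.5% need about 1,390 to 1,401 women by any account of how 932 arose.

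Third, the 10% covers non-adherence as well as loss, and non-adherent women stay in the intention-to-treat analysis. That is why the result is a range, not 33 events alone.

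Three stronger readings are tempting and are not supported.
- That no scenario whatever gives both 50 events and 80% power. Both arms at about 96.2% would: the hazard is −ln(0.962)/5 = 0.00775, p = 0.0600, and 838.8 × 0.0600 = 50.3 events. The inconsistency is with the plan's 97.5%.
- That accrual is planned as 60 women in two years and 872 in the next four, giving about 30 events and 61% power. The criterion "60 patients randomised by the end of year 2" in section 16.1.5 is a minimum for progression, not a forecast. The result is at most a slow-accrual sensitivity case.
- That waiting for 50 events would fit within the follow-up already planned. Scheduled follow-up is 10 years per woman. Under equal rates the 10-year event probability is 1 − 0.975² = 4.94%, which gives 41.4 events from 838.8 women (73% power) or 46.0 from 932 (77%).

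**Conclusion.** The concern holds on the plan's own inputs. The event target assumes a true hazard ratio of 1; the patient number fits only if Active Monitoring is at the margin. Under equal 97.5% rates, uniform accrual and analysis when all women have 5 years of follow-up, the design has about 33–37 events and 65–69% power, against the stated 50 and 80%. The type II error is about 31–35%, not 20%, and the time-based analysis in section 16.2.5 does nothing to correct this.

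The size is conditional on 97.5% being the rate for the full primary endpoint. If that figure leaves out deaths, events and power are higher by an amount the protocol does not allow anyone to fix.

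**What to change.** In section 16.2.6:
- State the 5-year Active Monitoring rate used to convert events to patients.
- Replace 50 events and 80% power with the figures under equal 97.5% rates: about 33–37 events and 65–69%, saying how the 10% is treated.
- State whether 97.5% covers death from any cause. If it does not, give the assumed death rate, restate the 5-year rates and the margin for the endpoint as defined, and recompute events and power.

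This costs protocol wording, one recalculation and possibly a less favourable stated power. No change to recruitment or conduct follows from the restatement itself.

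If the sponsor wants 80% power at equal 97.5% rates, about 1,390 to 1,401 women would be needed, or a later analysis. An event trigger in section 16.2.5 would need a calendar backstop and would depend on the extended data-linkage follow-up named in the synopsis, because 10 years per woman does not reach 50 events. Section 15 says that funding for follow-up is secured only to 10 years after the start of the trial, which is before the year-11 analysis, so the feasibility of any delay must be checked first.

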17 TRIAL ORGANISATIONAL STRUCTURE

17.1 Sponsor

The trial is sponsored by the University of Birmingham.

17.2 Coordinating Centre

The trial is being conducted under the auspices of the CRCTU, University of Birmingham according to their local procedures.

17.3 Quality of Life Coordinating Centre

The QoL data collection will be coordinated by SHORE- C.

17.4 Trial Management Group

The Chief Investigator, Co-investigators including the Trial Statistician, trial Radiologists, trial Pathologists, Quality of Life team, Trial Manager and Trial Coordinator will form the TMG. The TMG will be responsible for the day-to-day conduct of the trial. They will be responsible for the clinical set-up, promotion, on-going management of the trial, the interpretation of the results and preparation and presentation of relevant publications. The TMG will hold regular meetings (usually by teleconference). During the Feasibility Study, the TMG will hold monthly teleconferences.

17.5 Trial Steering Committee

The independent Trial Steering Committee (TSC) has been set up to oversee the trial. Membership will be composed of TMG members, representatives from the funders and at least one patient advocate. The TSC will meet shortly before commencement of the trial and annually (usually by teleconference), they will supervise the conduct of the trial, monitoring progress including recruitment, data completeness, losses to follow-up, and deviations from the protocol. They will make recommendations about conduct and continuation of the trial.

17.6 Data Monitoring Committee

Data analyses will be supplied in confidence to an independent DMC, which will be asked to give advice on whether the accumulated data from the trial, together with the results from other relevant research, justifies the continuing recruitment of further patients. The DMC will operate in accordance with a trial specific charter based upon the template created by the Damocles Group. The DMC is scheduled to meet one year after the trial opens to recruitment and then annually until 5 years after the last patient is recruited.

Page 37 of 48 Version 4.0, 15th March 2016

Additional meetings may be called if recruitment is much faster than anticipated and the DMC may, at their discretion, request to meet more frequently or continue to meet following completion of recruitment. An emergency meeting may also be convened if a safety issue is identified. The DMC will report directly to the TSC who will convey the findings of the DMC to the TMG, funder and sponsor. The DMC may consider recommending the discontinuation of the trial if the recruitment rate or data quality are unacceptable or if any issues are identified which may compromise patient safety. Specific progression criteria from the feasibility phase to the main trial are outlined in Section 16.1.5.

17.7 Finance

This is an investigator-initiated and investigator-led trial funded by the National Institute for Health Research (NIHR) Health Technology Assessment programme.

The Sponsor will pay Research Costs, as defined in the Clinical Site Agreement, to participating sites.

The trial has been adopted by the NIHR Cancer Research Network Portfolio.

18 ETHICAL CONSIDERATIONS

The trial will be performed in accordance with the recommendations guiding physicians in biomedical research involving human subjects, adopted by the 18th World Medical Association General Assembly, Helsinki, Finland, 1964, amended by the 48th WMA General Assembly, Somerset West, Republic of South Africa, 1996 (website: http://www.wma.net/en/30publications/10policies/b3/index.html) (see Appendix 3).

The trial will be conducted in accordance with the Research Governance Framework for Health and Social Care, the applicable UK Statutory Instruments, (which include the Data Protection Act 1998, Human Tissue Act 2008, Human Tissue (Scotland) Act 2006 and Good Clinical Practice (GCP). The protocol will be submitted to and approved by the Research Ethics Committee (REC) prior to circulation.

Before any patients are enrolled into the trial, the Principal Investigator at each site is required to obtain local R&D approval. Sites will not be permitted to enrol patients until written confirmation of R&D approval is received by the Trial Office.

It is the responsibility of the Principal Investigator to ensure that all subsequent amendments gain the necessary local approval. This does not affect the individual clinicians' responsibility to take immediate action if thought necessary to protect the health and interest of individual patients.

19 CONFIDENTIALITY AND DATA PROTECTION

Personal data recorded on all documents will be regarded as strictly confidential and will be handled and stored in accordance with the Data Protection Act 1998. With the patient's consent, their full name, date of birth, National Health Service (NHS) number, or in Scotland the Community Health Index (CHI), address, postcode, hospital number will be collected at trial entry to allow QoL questionnaires to be sent to patients' home address and to facilitate tracing through the Cancer Registries and the Health and Social Care Information Service (service formally provided by the Office of National Statistics) and to assist with long-term follow-up via other health care professionals e.g. patient's GP. Patients will be identified using only their unique TNO, initials and date of birth on the CRF and correspondence between the Trial Office and the participating site. However, patients are asked to give permission for the Trial Office to be sent a copy of their signed Informed Consent Form C, which will not be anonymised. This will be used to perform in-house monitoring of the consent process and will also be forwarded the patient's GP and possibly other health care professionals involved in the treatment of the patients.

The Investigator must maintain documents not for submission to the Trial Office (e.g. Patient Identification Logs) in strict confidence. In the case of specific issues and/or queries from the regulatory authorities, it will be necessary to have access to the complete trial records, provided that patient confidentiality is protected.

The Trial Office will maintain the confidentiality of all patient's data and will not disclose information by which patients may be identified to any third party other than the central radiology and pathology review team and those directly involved in the care of the patient and organisations for which the patient has given explicit consent for data transfer (e.g. Cancer Registries, laboratory staff). Representatives of the LORIS Trial team may be required to have access to patient's notes for quality assurance purposes but patients should be reassured that their confidentiality will be respected at all times.

Page **38** of **48** Version 4.0, 15th March 2016

20 INSURANCE AND INDEMNITY

University of Birmingham employees are indemnified by the University insurers for negligent harm caused by the design or co-ordination of the clinical trials they undertake whilst in the University's employment.

In terms of liability at a site, NHS Trust and non-Trust hospitals have a duty to care for patients treated, whether or not the patient is taking part in a clinical trial. Compensation is therefore available via NHS indemnity in the event of clinical negligence having been proven.

The University of Birmingham cannot offer indemnity for non-negligent harm.

21 PUBLICATION POLICY

Results of this trial will be submitted for publication in a peer reviewed journal. The manuscript will be prepared by the TMG and authorship will be determined by mutual agreement.

Any secondary publications and presentations prepared by Investigators must be reviewed by the TMG. Manuscripts must be submitted to the TMG in a timely fashion and in advance of being submitted for publication, to allow time for review and resolution of any outstanding issues. Authors must acknowledge that the trial was performed with the support of the University of Birmingham. Intellectual property rights will be addressed in the Clinical Study Site Agreement between Sponsor and site.

Page **39** of **48** Version 4.0, 15th March 2016

23 APPENDIX 1 – DEFINITION OF ADVERSE EVENTS

Adverse Event

Any untoward medical occurrence in a patient or clinical trial subject participating in the trial, which does not necessarily have a causal relationship with the treatment received.

Comment:

An AE can therefore be any unfavourable and unintended sign (including abnormal laboratory findings), symptom or disease temporally associated with the use of a medicinal product, whether or not related to the medicinal product.

Related Event

An event which resulted from the administration of any of the research procedures.

Serious Adverse Event

An untoward occurrence that:

- Results in death unrelated to the original DCIS diagnosis
- Is life-threatening*
- Requires hospitalisation** or prolongation of existing hospitalisation
- · Results in persistent or significant disability or incapacity
- Consists of a congenital anomaly/ birth defect
- Or is otherwise considered medically significant by the Investigator***

Comments:

The term severe is often used to describe the intensity (severity) of a specific event. This is not the same as serious, which is based on patients/event outcome or action criteria.

- * Life threatening in the definition of an SAE refers to an event in which the patient was at risk of death at the time of the event; it does not refer to an event that hypothetically might have caused death if it were more severe.
- **Hospitalisation is defined as an unplanned, formal inpatient admission, even if the hospitalisation is a precautionary measure for continued observation. Thus, hospitalisation for protocol treatment (e.g. line insertion), elective procedures (unless brought forward because of worsening symptoms) or for social reasons (e.g. respite care) are not regarded as an SAE.
- *** Medical judgment should be exercised in deciding whether an AE is serious in other situations. Important AEs that are not immediately life threatening or do not result in death or hospitalisation but may jeopardise the subject or may require intervention to prevent one of the other outcomes listed in the definition above, should be considered serious.

Unexpected and Related Event

An event which meets the definition of both an Unexpected Event and a Related Event.

Unexpected Event

The type of event that is not listed in the protocol as an expected occurrence.

24 APPENDIX 2 - COMMON TOXICITY CRITERIA GRADINGS

Toxicities will be recorded according to the National Cancer Institute Common Terminology Criteria for Adverse Events (NCI CTCAE), version 4.0.

The full NCI CTCAE document is available on the NCI website, the following address was correct when this version of the protocol was approved:

http://ctep.cancer.gov/protocolDevelopment/electronic_applications/ctc.htm#ctc_40

Page **44** of **48** Version 4.0, 15th March 2016

25 APPENDIX 3 – WMA DECLARATION OF HELSINKI

WORLD MEDICAL ASSOCIATION DECLARATION OF HELSINKI Recommendations guiding physicians in biomedical research involving human subjects

Adopted by the 18th World Medical Assembly

Helsinki, Finland, June 1964 and amended by the

29th World Medical Assembly, Tokyo, Japan, October 1975 35th World Medical Assembly, Venice, Italy, October 1983 41st World Medical Assembly, Hong Kong, September 1989 and the

48th General Assembly, Somerset West, Republic of South Africa, October 1996

INTRODUCTION

It is the mission of the physician to safeguard the health of the people. His or her knowledge and conscience are dedicated to the fulfilment of this mission.

The Declaration of Geneva of the World Medical Association binds the physician with the words, "The Health of my patient will be my first consideration," and the International Code of Medical Ethics declares that, "A physician shall act only in the patient's interest when providing medical care which might have the effect of weakening the physical and mental condition of the patient."

The purpose of biomedical research involving human subjects must be to improve diagnostic, therapeutic and prophylactic procedures and the understanding of the aetiology and pathogenesis of disease.

In current medical practice most diagnostic, therapeutic or prophylactic procedures involve hazards. This applies especially to biomedical research.

Medical progress is based on research which ultimately must rest in part on experimentation involving human subjects.

In the field of biomedical research a fundamental distinction must be recognized between medical research in which the aim is essentially diagnostic or therapeutic for a patient, and medical research, the essential object of which is purely scientific and without implying direct diagnostic or therapeutic value to the person subjected to the research.

Special caution must be exercised in the conduct of research which may affect the environment, and the welfare of animals used for research must be respected.

Because it is essential that the results of laboratory experiments be applied to human beings to further scientific knowledge and to help suffering humanity, the World Medical Association has prepared the following recommendations as a guide to every physician in biomedical research involving human subjects. They should be kept under review in the future. It must be stressed that the standards as drafted are only a guide to physicians all over the world. Physicians are not relieved from criminal, civil and ethical responsibilities under the laws of their own countries.

I. BASIC PRINCIPLES

- Biomedical research involving human subjects must conform to generally accepted scientific principles and should be based on adequately performed laboratory and animal experimentation and on a thorough knowledge of the scientific literature.
- 2. The design and performance of each experimental procedure involving human subjects should be clearly formulated in an experimental protocol which should be transmitted for consideration, comment and guidance to a specially appointed committee independent of the investigator and the sponsor provided that this independent committee is in conformity with the laws and regulations of the country in which the research experiment is performed.

Page **45** of **48** Version 4.0, 15th March 2016

- 3. Biomedical research involving human subjects should be conducted only by scientifically qualified persons and under the supervision of a clinically competent medical person. The responsibility for the human subject must always rest with a medically qualified person and never rest on the subject of the research, even though the subject has given his or her consent.
- 4. 4. Biomedical research involving human subjects cannot legitimately be carried out unless the importance of the objective is in proportion to the inherent risk to the subject.
- 5. Every biomedical research project involving human subjects should be preceded by careful assessment of predictable risks in comparison with foreseable benefits to the subject or to others. Concern for the interests of the subject must always prevail over the interests of science and society.
- 6. The right of the research subject to safeguard his or her integrity must always be respected. Every precaution should be taken to respect the privacy of the subject and to minimize the impact of the study on the subject's physical and mental integrity and on the personality of the subject.
- 7. Physicians should abstain from engaging in research projects involving human subjects unless they are satisfied that the hazards involved are believed to be predictable. Physicians should cease any investigation if the hazards are found to outweigh the potential benefits.
- 8. In publication of the results of his or her research, the physician is obliged to preserve the accuracy of the results. Reports of experimentation not in accordance with the principles laid down in this Declaration should not be accepted for publication.
- 9. In any research on human beings, each potential subject must be adequately informed of the aims, methods, anticipated benefits and potential hazards of the study and the discomfort it may entail. He or she should be informed that he or she is at liberty to abstain from participation in the study and that he or she is free to withdraw his or her consent to participation at any time. The physician should then obtain the subject's freely-given informed consent, preferably in writing.
- 10. When obtaining informed consent for the research project the physician should be particularly cautious if the subject is in a dependent relationship to him or her or may consent under duress. In that case the informed consent should be obtained by a physician who is not engaged in the investigation and who is completely independent of this official relationship.
- 11. In case of legal incompetence, informed consent should be obtained from the legal guardian in accordance with national legislation. Where physical or mental incapacity makes it impossible to obtain informed consent, or when the subject is a minor, permission from the responsible relative replaces that of the subject in accordance with national legislation. Whenever the minor child is in fact able to give a consent, the minor's consent must be obtained in addition to the consent of the minor's legal guardian.
- 12. The research protocol should always contain a statement of the ethical considerations involved and should indicate that the principles enunciated in the present Declaration are complied with.

II. MEDICAL RESEARCH COMBINED WITH PROFESSIONAL CARE (Clinical Research)

- 1. In the treatment of the sick person, the physician must be free to use a new diagnostic and therapeutic measure, if in his or her judgement it offers hope of saving life, reestablishing health or alleviating suffering.
- 2. The potential benefits, hazards and discomfort of a new method should be weighed against the advantages of the best current diagnostic and therapeutic methods.
- 3. In any medical study, every patient including those of a control group, if any should be assured of the best proven diagnostic and therapeutic method. This does not exclude the use of inert placebo in studies where no proven diagnostic or therapeutic method exists.

Page **46** of **48** Version 4.0, 15th March 2016

- 4. The refusal of the patient to participate in a study must never interfere with the physician-patient relationship.
- 5. If the physician considers it essential not to obtain informed consent, the specific reasons for this proposal should be stated in the experimental protocol for transmission to the independent committee (I, 2).
- 6. The physician can combine medical research with professional care, the objective being the acquisition of new medical knowledge, only to the extent that medical research is justified by its potential diagnostic or therapeutic value for the patient.

III. NON-THERAPEUTIC BIOMEDICAL RESEARCH INVOLVING HUMAN SUBJECTS (Non-Clinical Biomedical Research)

- 7. In the purely scientific application of medical research carried out on a human being, it is the duty of the physician to remain the protector of the life and health of that person on whom biomedical research is being carried out.
- 8. The subject should be volunteers either healthy persons or patients for whom the experimental design is not related to the patient's illness.
- 9. The investigator or the investigating team should discontinue the research if in his/her or their judgement it may, if continued, be harmful to the individual.
- 10. In research on man, the interest of science and society should never take precedence over considerations related to the wellbeing of the subject.

Page 47 of 48 Version 4.0, 15th March 2016

